### **Summary of Prior Work**

A. Safety testing in athletes has been approved by the local IRB and was completed in the Cincinnati Children’s Hospital Human Performance Laboratory (*Study ID: 2013-2240; PI: [name]*). Evaluation of monitored vital signs, biomechanics, cardiorespiratory capacity, postural control, dynamic stabilization, reactive index, concentration and cognition, memory, strength and power in a population of athletes showed no statistically significant adverse effect of wearing a mild jugular vein compressive neck collar compared to a sham arm band.(Myer 2013) Cumulatively, the pre and post safety measures indicate that neurologic parameters of executive function, eye hand coordination, balance, memory and reaction times were unchanged following two hours of physical testing wearing the collar prototype. Acceptance of the compression collar was not different in physiological biomarker response to the non-collared condition during maximal oxygen uptake and maximum effort power testing.(Myer 2013)

B. Magnetic Resonance Elastography was established at CCHMC in collaboration with The Mayo Clinic to support these studies. Under jugular vein compression with the collar, all participants tolerated the procedure without any untoward effects. The preliminary studies of dynamic shear strain showed no consistent pattern of wave propagation and elasticity placed upon the vascular and cranial tissues. Analysis of these data continues.

C. We studied 410 participants (ages 12 to 68 years of age) via a middle ear power analysis (MEPA) with and without the compression collar, and no complaints or untoward

effects were noted and no decline in the auditory perception was recorded. The expected changes of reduced Acoustic Reflectance of the inner ear and middle ear (indicative of reduced compliance) were noted only in subgroup analysis of those with jugular vein compression. The results of this study indicate that the neck compression collar prototype may have the potential to safely reduce energy impartation into cranial structures (i.e., the inner ear); however, further work is needed with advanced collar designs to establish this effect.

D. fMRI and CO2 reactivity was performed on 12 adults before and after application of jugular vein compression. Results comparing before and after jugular vein compressions (with the collar) yielded no alterations in O2 uptake or glucose metabolism to any portion of the brain.(Fisher 2013).

E. An *in vivo* clinical trial was approved by CCHMC IRB and was completed in the Cincinnati Children’s Hospital Human Performance Laboratory and Radiology Department (Study ID: 2014-5009; PI: [name]) An *in vivo* clinical trial was performed in hockey players of the proposed intervention device used during sporting competitions to test its effect in ameliorating neuroanatomical and neurophysiological changes to the brain using two widely accepted techniques [diffusion tensor imaging (DTI), and event related potentials (ERPs) utilizing electroencephalography.](Reches 2014) For athletes in the non-intervention group, radial diffusivity (RD, DTI parameter associated with white matter structural integrity(Song 2003; Song 2005)) increased significantly from pre-season to mid-season. By comparison, the athletes in the intervention group did not show a significant change in RD with similar accumulated g-force head impacts. In kind, ERP analysis showed concomitant changes in brain network dynamics in the non-intervention group—the level of change was strongly correlated with the accumulated g-force of the collisions, whereas the intervention group showed no significant change. These group differences indicate that mild jugular vein compression may provide protection from the detrimental effects of collisions and resultant brain injury. These prospective longitudinal data utilized an internal (*in vivo*) approach and demonstrate, for the first time, that it is possible to protect the brain from sports related head impacts.

#### (4) STUDY DESIGN:

The current project will be designed following a prospective longitudinal study design. All MRI scanning will be performed on a 3 Tesla Philips Achieva MRI scanner located in Imaging Research Center (IRC) in the Cincinnati Children’s Hospital Research Foundation (CCHRF). Sedation will not be used for any of the test visits. The entire MRI series, including anatomical imaging, DTI, resting state fMRI, SWI, HARDI, ASL and BOLD will be completed in 65 minutes or less (see Table 1 for detailed specifications). All functional and neurocognitive testing will be performed at the Cincinnati Children’s Hospital Human Performance Laboratory.

**Table 1.** Image sequence, mode and analysis. Imaging will be completed in 60 minutes or less.

Sequence	Time (min)	Mode	Analysis
3D T1	5	Anatomy	Visual / Volumetrics
DTI	11	WM microstructure	Visual/ROI/TBSS or

			other
rs-fMRI	10	Connectivity/networks	Quantitative
SWI	6	Hemorrhagic Injury	Visual (Automated analysis)
HARDI	10-12	WM microstructure	Quantitative

**(5) DURATION:**

The study recruitment and intervention will occur during one season. Each participant will participate in 2 planned study visits that may take up to 2 hours. Data analysis will continue for a 2 year period following the final enrollment.

**(6) SELECTION & RECRUITMENT OF PARTICIPANTS:**

The purpose of the present study is to generate pilot data for effect size estimation and power analysis for future study. The group size proposed in the aims was determined empirically based on previous neuroimaging studies and study designs reported in the literature. The sample size proposed in this pilot study will not warrant extensive statistical analysis to test the listed hypothesis. This study is expected to lead to an accurate estimate of effect size and variability so that future studies can be designed more rigorously.

We will recruit up to 60 study participants. The participants (age 14-19 years old) will be recruited from a local school district and local sports clubs and teams. Participants will be recruited using a top-down approach. We have gained the consent and the cooperation of the school district administrations. Presentations and letters from the research team will be given to each participating school to detail the participation requirements and study risks. The high-risk sports which utilize helmets during competition will allow for measurement devices to be embedded in the headgear and will not affect play or fit of equipment. By the nature of the sports selected, it is likely this study will primarily include males, however if any female meets inclusion criteria on the team selected, she will be included in the investigation. Questions regarding participation will be answered during the presentations or through e-mail or phone. Participants will be contacted via telephone to further explain the study, answer any additional questions and to enroll them in the study. The participants and parents/guardians who voluntarily agree to participate will be scheduled to complete the pre-participation testing. The participant and parent/guardian will read and sign the "Consent to Participate in a Research Study" form, approved by the Institutional Review Board of Cincinnati Children's Hospital. If the participant and parent/guardian does not read or sign the form, they will not participate in the study. Once the potential study participants/school teams are identified, they will be allocated to one of two groups: 1) Device wearing during the season or 2) Non-device wearing during the season. This research does not mandate that the participant maintains participation in their sport. The desire to participate in the sporting event is an independent, personal decision separate from the decision to enter into this study. If any athlete chooses to stop participation in the sporting activity then they will also be withdrawn from the study, due to no longer meeting inclusion criteria.

Inclusionary criteria include:

- Normal healthy volunteer
- Able to provide written consent

- Must be 14 years or older and a participant on varsity level high school football team

Exclusionary criteria include:

- Unable to provide written consent
- History of neurological deficits, previous cerebral infarction, or severe head trauma as indicated through pre-season screening:
- Medical contraindications to restriction of venous outflow via the internal jugular veins (known increased intracerebral pressure, metabolic acidosis or alkalosis)
- Glaucoma (Narrow Angle or Normal Tension)
- Hydrocephalus
- Recent penetrating brain trauma (within 6 months)
- Known carotid hypersensitivity
- Known increased intracranial pressure
- Central vein thrombosis
- Any known airway obstruction
- Any known seizure disorder

#### **(7) PROCESS OF OBTAINING CONSENT**

Once a participant is identified as a potential participant, is contacted by a CCHMC/Sports Medicine representative and verbally agrees to participate, the process to obtain consent will begin. A copy of the informed consent will be provided to the participant at this time. The study coordinator will review the informed consent and the participant will have an opportunity to ask any questions regarding the study and/or the study protocol. At that time, the participant will be given time to decide whether or not they wish to participate and if so, asked to sign the informed consent. Once the signature is obtained, the participant will be given a copy of the consent and testing will commence. At no time will the participant be coerced into participation. Receiving the informed consent prior to enrollment will allow the participants to review the study information prior to participation in the study. This will aid the participant to make an informed, unforced decision regarding election to participate in the study.

Because we will be testing teens, we will be using the Parent Consent Form to obtain both the participant assent and the parent consent. The participants and their parents will be given adequate time to review the study materials and ask questions. If they choose to participate, the patient and parent will sign the IRB approved consent forms. It will be made clear to the patient and their parents that participation in the study is voluntary.

In the event that a parent or guardian will not be present at the scheduled testing appointment, consent/assent forms will be provided ahead of time for review. The coordinator will ensure that all necessary forms have been signed prior to any data collection.

#### **(8) STUDY PROCEDURES:**

**Location I – Brain Imaging-Performed at CCHMC Imaging Research Center**

##### **MR imaging data Acquisition**

Magnetic Resonance Imaging (MRI), including sequences outlined in Table 1 are all based on the concept of using magnetic fields and radio waves to make chemical, anatomical and physiological assessments with in the living tissue. This technology has been utilized for diagnostic and research purposes since the early 1980s.

This testing will consist of a minimum of 2 MRI sessions (preseason, and post season) and additional scans following any clinically diagnosed concussions, all inside a 3T scanner at the CCHMC Imaging Research Center. During the acquisition of MR images, the study participants will lie on the scanner table. For most portions of MR acquisition, the study participants will only be instructed to lie still. For other parts of the acquisition, study participants will be asked to answer questions that will assess their cognitive ability and working memory. Participants will be allowed to communicate with the MR operator via an always-on, two-way intercom at any time. In addition, the participants have a hand-held air ball to squeeze in the event that they elect to be removed from the magnet immediately. The study participants have control over their presence in the magnet, which in turn tends to minimize feelings of claustrophobia. As magnetic resonance imaging employs the use of strong magnets, patients will receive a standard preoperative screening questionnaire regarding the potential for ferromagnetic objects within their bodies to ensure their safety during the study. Participants will be screened for MRI specific contraindications such as:

- Braces or permanent metal dental work
- Insulin pump
- Cardiac pacemaker
- Cochlear implants
- Hearing aids
- Aneurysm clips
- Orthopedic pins, wires, screws, or plates
- Any other exclusionary criteria as documented on the MRI safety screening poster included with recruitment materials

Those participants with any aforementioned contraindication will be excluded from the imaging portion of the study but will still be eligible to participate in the rest of the study procedures.

## **Location 2 -Physical and Cognitive Testing Performed at CCHMC Human Performance Laboratory**

### ***Station I: Anthropometric Measurements.***

Anthropometric measures will be recorded at Station IV. Height, weight, leg length and body composition (bioelectrical impedance) will be recorded and body mass index (BMI) calculated.

**Height:** A measure of height will be recorded with a digital stadiometer (accurate to 0.25 cm).

**Weight:** A measure to the nearest 0.5 kg will be taken on a calibrated physician scale with the participants' shoes off.

**Neck Measurement:** We will measure the circumference of your neck with a measuring tape.

### ***Station II – Neurocognitive Assessment***

Neurocognitive testing will take place as participants will take the web version of ImPACT (Immediate Post-Concussion Assessment and Cognitive Testing). Neurocognitive testing is utilized in concussion management and ImPACT provides measures of verbal and visual memory, processing speed and reaction time. All participants will complete web-based ImPACT prior to participation in each experimental session and following any diagnosed concussion injury.

### ***Station III - Reaction Time Testing on Smart Phone***

The participants will be asked to perform simple visual and auditory reaction time testing using a customized smart phone application in which a tone plays/the screen changes color and the participant has to remove his finger as quickly as possible over 30 response trials.

### ***Station IV – Oculomotor Assessment***

All participants will sit in front of a desktop monitor. During this process, the participant will look at several points in order to calibrate the desk-top eye tracker (Tobii X2 60). All participants will participate in three oculomotor performance tests: (1) a reflexive saccade test, (2) a self-paced saccade test, and (3) a smooth-pursuit tracking test. All tests will be presented on a PC monitor approximately 1.5 m away from participant, and stimuli will be automated using customized *MATLAB* (Mathworks, Natick, MA) routines.

*Reflexive Saccades.* Reflexive saccades will be tested as participants track discrete target motion that will jump randomly by 14, 16, 18, 20, 22, or 24° on the screen in a horizontal direction, at intervals varying pseudo randomly between 1.0 and 2.0 s. The current fixation target will be extinguished at the same time as the next peripheral target appears. An auditory tone will also sound concurrently with each target jump. The test sequence will include 49 trials and all participants will be instructed to follow the targets as quickly and accurately as possible. Dependent measures for reflexive saccades will include: (1) saccade latency (ms), (2) saccade velocity (°/s), (3) mean absolute position error of the final eye position, (4) gain of the primary saccade, and (4) gain of the final eye position.

*Self-paced saccades.* Self-paced saccades will be assessed as the participant glances back and forth as quickly and accurately as possible between two constantly visual targets at  $\pm 15^\circ$  horizontally from one another. This test will take 30 s per trial and the participant will perform 4 trials. The dependent measures will be: (1) the number of refixations within 30 s, and (2) the mean intersaccadic interval (ms).

*Smooth pursuit tracking.* Smooth pursuit tracking will be tested as the participant attempts to fixate and track the center of a horizontally moving stimulus on the computer screen. The stimulus will include a target moving in a predictable sinusoidal pattern with a peak velocity of 20, 40, and 60°/s and a target moving in a random pattern with a mean peak velocity of 80°/s. The duration of each test will be 40 s and this assessment will consist of six trials (2 per condition). Dependent measures for smooth pursuit tracking will include: (1)

average eye peak velocity ( $^{\circ}/s$ ) after removal of all saccades from the tracking performance, and (2) the tracking lag (ms). Total oculomotor testing time will take approximately 10 minutes, and all eye data will be recorded using Tobii Studio software and will be sampled at 60 Hz.

*Smooth pursuit tracking and occlusion.* Smooth pursuit tracking will also be tested as the participant attempts to track the center of a horizontally moving stimulus prior to and after it becomes occluded as it moves on the computer screen. The stimulus will be the same as the smooth pursuit tracking mentioned above, however for 1000 ms, the target will become occluded and the participants will have to resume tracking the target object once it comes back out from behind the occluder.

### ***Station V – Electroencephalogram (EEG)***

The following cognitive tests will be performed while EEG/ERP data is collected:

**Auditory oddball task.** The oddball task is a classic EEG paradigm that has been extensively used for many years, in numerous studies and in many neurological patient populations. It is considered to involve executive functions, attention and memory processes. The main ERP components are N100 (low level stimulus processing) and P300 (attention allocation and stimulus evaluation), which is maximal at fronto-central areas for novel stimuli and centro-parietal for Target stimuli. In this task sounds are presented, at an average rate of 1 every 1.5sec. A total of 80% of the sounds ("standard") are tones of repeating frequency and intensity. A total of 10% of the sounds ("target") are tones of another frequency to which participants respond by pressing a button. The remaining 10% of sounds ("novel") are multi-frequency sounds, different for each trial. The test takes approximately 11 min to complete.

**Go-No Go test.** The Go-No Go paradigm is among the most well-established tests of response inhibition to perceptual stimuli. Go-No Go tasks involve the presentation of a continuous series of "Go" or target cues to which participants are asked to respond as quickly as possible, and "No Go" or distracter cues that require participants to inhibit motor responses. Studies involving ERP have identified a negative-going component occurring at 200 – 400 ms following the No Go stimulus known as the "No Go N2", which occurs maximally at frontal-central scalp locations. On No Go trials, the N2 is followed by a positive-going shift. This positive complex, termed the "No Go P3", also occurs maximally at frontal-central scalp sites and is typically seen 300 – 700 ms following the No Go stimulus. The Go-No Go task takes approximately 9 min to complete.

**Resting EEG.** 4 min resting EEG will be recorded at the end of the tasks, with participant fixating at the center of the screen, 2 min with eyes open and 2 min with eyes closed.

### **Injury Surveillance**

*Device and Compliance Acceptance:* The study coordinator will be responsible for providing the appropriate intervention (device or no-device) to each team based on their random

be reported according to criteria outlined in recent multi-investigator consensus documents (McCrary, 2013). The incidence of concussion will be calculated in this study using cases identified through two primary mechanisms: 1) Monitoring of concussion injuries and time missed from planned physical activity by the AT for each team, and 2) weekly inquiries to each coach by the Study Coordinator as to whether any participants are missing time from activity due to concussion. This dual query approach enables the Study Coordinator to cross check the injury and exposure data collected to improve the accuracy of the data. The data secured from the coach regarding each athlete's participation in individual practices and games combined with accelerometer exposure to impacts allows the research team to capture robust individual athlete exposures rather than just combined team exposures.

The athletic trainer will evaluate any athlete for whom a concussive event has been observed (within 24 hours). If criteria for concussive sequelae are not met, the athlete is cleared for return to play. In the event of a positive concussion evaluation by the AT, an MD will perform a second evaluation. Should the MD concur with the AT on a positive evaluation, a diagnosis of isolated concussion is made and the athlete is removed from play and participant is referred for to a post-concussion evaluation. The diagnosing physician will be blinded to the experimental treatment of the study participants.

Post-concussion and post season testing consists of the same battery of tests as performed for pre-season testing, which allows for direct comparison between typical and concussed data. In addition, concussed athletes will complete the Post-Concussion Symptom Inventory (PCSI) questionnaire at the beginning of the testing session and repeated at the conclusion of this session. Additional neurologic testing is done on athletes with confirmed or suspected concussion to narrow down neuro-systems involved. Concussion evaluations will be repeated as needed until the MD is satisfied that the athlete has fully recovered from the concussion. This includes a return to baseline at rest, no exam abnormalities, and baseline symptoms with sports-specific exertion; whereupon the athlete will be cleared for return to activity. The amount of time the athlete was considered unfit to play will also be considered as one of the endpoints of this study. If any athlete chooses to stop participation in the sporting activity following a concussion then they will also be withdrawn from the study, due to no longer meeting inclusion criteria.

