This study will investigate the effectiveness of this device in high school athletes playing a collision sport such as football. The use of helmets during such a high-risk sport will allow for collision measurement devices to be embedded in the helmet and will not affect play or fit of equipment. Athletes participating in this study will be randomly assigned to one of two groups: 1) Device wearing during the season or 2) Non-device wearing during the season. By the nature of the sport selected, it is likely this pilot study will primarily include males, however if any female meets inclusion criteria on the team selected, she will be included in this investigation. The helmets of all participants will be outfitted with an accelerometer which will measure the magnitude of every impact to the head sustained by the athlete. Effectiveness of the device will be determined via differences in longitudinal brain imaging and functional testing following competitive football participation. A subset of athletes who report a diagnosed concussion will also receive additional brain neuroanatomical and neurophysiological testing within a week following the diagnosed concussive event. At each of these time points participants will also undergo various neurocognitive assessments outlined below.

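### The plan does not settle whether athletes or teams are allocated, and no analysis names a team term; if teams are allocated and teammates' outcomes are correlated, athlete-level intervals are too narrow

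*Combined protocol and SAP*

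**What the plan says.** Three places describe allocation, and they differ.

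- Section (1), Abstract: "Athletes participating in this study will be randomly assigned to one of two groups". The unit is the athlete.
- Section (6), Selection and Recruitment: "Once the potential study participants/school teams are identified, they will be allocated to one of two groups". The unit is left open, and this sentence does not say that the allocation is random.
- Section (8), Injury Surveillance: the coordinator is responsible for "providing the appropriate intervention (device or no-device) to each team based on their random". The sentence breaks off there in the extracted text. The visible words name the team.

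The number of teams is not settled either. The Abstract speaks of one ("if any female meets inclusion criteria on the team selected"), and section (6) uses the same singular. But section (6) also says that presentations and letters "will be given to each participating school", and Injury Surveillance plans "weekly inquiries to each coach by the Study Coordinator".

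In section (9), the ANCOVA uses time and condition. The ANOVAs for reaction time and oculomotor measures use group, session and task condition. The voxel-based imaging comparison uses group and longitudinal change. The candidate predictors are all athlete-level, although the list is open. Random effects are mentioned only for the secondary Poisson model, with no grouping factor named. The same section sets two-sided tests at 0.05 and plans extensive use of 95% intervals to express efficacy.

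**The concern.** The unit of allocation determines the standard error of the collar effect. Teammates share coaching, schedule, opponents and style of play, so their seasonal changes may be correlated. If whole teams receive or do not receive the collar, that correlation adds to the variance of the difference between arms, and a model that treats athletes as independent does not see it.

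Section (6) plays down testing ("The sample size proposed in this pilot study will not warrant extensive statistical analysis to test the listed hypothesis"), so the main stake is not a p-value. It is the precision attached to the estimate passed to the next study: "This study is expected to lead to an accurate estimate of effect size and variability". An interval that is too narrow would make that estimate look firmer than it is. With one team per arm the problem is worse, because no model can separate a collar effect from a team difference in seasonal change.

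**Working it through.** The plan gives no power, SD, ICC, allocation ratio or settled team count, so it has no figure of its own to reproduce.

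**Inputs from the protocol:** up to 60 participants (section 6); two-sided 0.05 and 95% intervals (section 9).

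**Assumptions, not in the documents:** all 60 recruited, 30 per arm, k equal teams of m = 60/k, total SD = 1, and ICC of the analysed outcome 0, 0.01, 0.05 or 0.10.

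**1. Athlete-level interval.** SE = √(4/60) = 0.258 SD. Half-width = t(58) × 0.258 = 0.517 SD.

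**2. Teams allocated, athletes analysed as independent.** The design effect is DE = 1 + (m − 1) × ICC. The approximate true size of a nominal 5% test is 2 × (1 − Φ(1.96/√DE)). For four teams and ICC 0.05, DE = 1 + 14 × 0.05 = 1.70 and √DE = 1.304, so the size is 0.133. Coverage of a nominal 95% interval is then about 86.7%, and the effective sample size is 60/1.70 = 35.

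Each cell below gives ICC 0.01 / 0.05 / 0.10. At ICC 0 the size is 0.05 throughout.

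| Teams | DE | Size, formula | Size, simulated | Reported SE / true SE |
|---|---|---|---|---|
| 2 | 1.29 / 2.45 / 3.90 | 0.084 / 0.210 / 0.321 | 0.084 / 0.217 / 0.339 | 0.873 / 0.621 / 0.479 |
| 4 | 1.14 / 1.70 / 2.40 | 0.066 / 0.133 / 0.206 | 0.066 / 0.135 / 0.212 | 0.931 / 0.755 / 0.627 |
| 6 | 1.09 / 1.45 / 1.90 | 0.060 / 0.104 / 0.155 | 0.060 / 0.105 / 0.159 | 0.953 / 0.820 / 0.711 |
| 10 | 1.05 / 1.25 / 1.50 | 0.056 / 0.080 / 0.110 | – | – |

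Simulations used 200,000 trials per cell.

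**3. Teams allocated, teams analysed.** With the true SE, the half-width is t(k − 2) × √(4 × DE/60). In practice the SE is estimated on few degrees of freedom, so the expected width is smaller, by a factor of 0.940 on 4 df and 0.886 on 2 df. For ICC 0 / 0.01 / 0.05 / 0.10:

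- Six teams: 0.717 / 0.748 / 0.863 / 0.988, times 0.940, gives 0.67 / 0.70 / 0.81 / 0.93 SD.
- Four teams: 1.111 / 1.186 / 1.448 / 1.721, times 0.886, gives 0.98 / 1.05 / 1.28 / 1.52 SD.
- Two teams: 0 df, so no interval exists.

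The ICC 0 values show that much of the widening comes from the small number of teams and not from the correlation.

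**4. The SD passed on.** The expected pooled within-arm SD is √((1 − ICC) + ICC × (30 − m)/29). For ICC 0.01 to 0.10 it is low by 0.2-1.6% with six teams, 0.2-2.4% with four and 0.5-5.1% with two.

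**5. Athletes randomised within teams, team left out.** The ratio of the SE without a team term to the SE with one is √(((1 − ICC) + ICC × (m/2) × (k − 1)/29)/(1 − ICC)). For ICC 0.01 to 0.10 it is 1.003-1.028 with two teams, 1.004-1.042 with four and 1.004-1.047 with six. Simulated test size for two and six teams is 0.041-0.049 without the team term and 0.049-0.050 with it. The test is slightly conservative and remains valid.

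**The case against.** The strongest reply is that the plan may simply randomise athletes. The Abstract holds the only complete sentence on random assignment, and its subject is athletes. The singular team in the Abstract and in section (6) points the same way, since with one team only athletes can be randomised. Supplying a collar to a team can describe delivery, and the missing end of that sentence may have settled the matter. All this stands, and it is why the point is conditional. It does not remove the conflict, because section (6) still names school teams as a possible unit and nothing in the available text resolves it.

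The harm is also doubly conditional: teams must be allocated and the ICC must be positive. That stands too. The 34% figure belongs to two teams at ICC 0.10; with ten teams at ICC 0.01 the size is 5.6%. The documents support no particular ICC for seasonal change.

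The pilot label lowers the weight of the tests, but not of the intervals that the plan intends to report.

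A reader might infer that this is a cluster-randomised trial analysed wrongly, that its false-positive rate is as high as a third, or that the plan never gives the number of teams. The documents support none of these. The unit is unresolved, the error rates rest on assumed inputs, and the team count may stand in text that was lost. Nor is the SD for planning seriously distorted, since it is low by about 5% at most over this range.

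**Conclusion.** The point holds as an unresolved inconsistency with a conditional consequence. The descriptions of allocation do not agree, and no planned analysis names a team term. Under athlete randomisation the cost is a loss of precision of less than 5% in the SE over the range examined. Under team allocation with positive ICC, athlete-level tests and intervals are too optimistic, from barely (ten teams, low ICC) to severely (two teams, ICC 0.10). With one team per arm the collar effect is not separable from a team difference in seasonal change; analysing change largely removes stable team differences but not that one.

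The direction of the error follows from the design. Its size rests wholly on the assumed team count, equal teams, 1:1 allocation and ICC. It should be fixed; confidence is medium because the unit actually intended is unknown.

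**What to change.** Reconcile the Abstract, section (6) and Injury Surveillance to one unit of allocation. State the number of teams, or cross-refer if it is given elsewhere. Then match the analysis in section (9) to that unit:

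- **Athletes randomised within teams:** add team as a fixed effect to the ANCOVA and ANOVAs. In the Poisson model this is optional, because sparse concussion counts may leave a team effect inestimable. With a single team no term is needed. The cost is one degree of freedom per additional team (residual df 57 with two teams and 53 with six, against 58).
- **Teams allocated:** analyse team means, or use a team random effect with small-sample degrees of freedom (number of teams minus 2, or Kenward-Roger), for all between-arm comparisons, including the imaging group analysis. The cost is wider intervals, as shown in step 3, and revision of several analyses.
- **One team per arm:** report the comparison descriptively and state that a collar effect cannot be separated from a team difference in seasonal change.

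No change to the unit of allocation or to trial conduct is proposed.
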